## 9.2 Rationale for study design and dose groups

A Single Ascending Dose (SAD) design was chosen for the evaluation of the cardiac safety of Modufolin® for Injection, 100 mg. The adaptive study design allows for flexible dose escalation and involves careful monitoring of the subject's well-being. The study will also provide important PK data to support the design of further studies, both in healthy volunteers and in patients. The time points for PK blood sampling were selected based on data obtained from previous clinical studies (see summary of PK data in Appendix 18.3). After dose administration, the time points for extraction of ECG data are paired with PK blood sampling.

A placebo control will be used to establish the frequency and magnitude of changes in endpoints that may occur in the absence of active treatment.

Randomization will be used to minimize bias in the assignment of subjects to dose groups and to increase the likelihood that known and unknown subject attributes (e.g., demographic and baseline characteristics) are evenly balanced across treatment groups.

Blinded treatment will be used to reduce potential bias during data collection and evaluation of endpoints.

The primary objective of the current clinical study is to evaluate potential effects on ECG parameters following single doses administration of Modufolin® for Injection, 100 mg in healthy volunteers. To allow exclusion of a small effect on the QT interval, serial ECG monitoring is implemented in the study, a highly precise ECG methodology will be used and data will be analysed using exposure response analysis.

Three dose levels of Modufolin® for Injection, 100 mg will be studied (200, 350 and 500 mg/m^2), including two supratherapeutic doses, which will obviate the need for a positive control in the study. Based on current data the expected clinical dosing regimen in future clinical trials in metastatic colorectal cancer patients (lead indication) is 120 mg/m^2 Modufolin® for Injection, 100 mg. Doses of Modufolin® up to 500 mg/m^2/day have been administered to patients in a previous non-IND clinical study with no safety concerns (ISO-MC-091).

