### 10.8 Randomisation

Subjects in each cohort will be randomized to receive either placebo (3 subjects) or active treatment (8 subjects).

The randomization list will be generated by CTC or delegate and provided to the packing company. The original randomization list will be kept in a sealed envelope by the randomizer. Sealed treatment code envelopes will be kept by CTC and the Sponsor.

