## 11.6 Treatment administration

The pre-defined dose levels are 200, 350 and 500 mg/m^2 of Modufolin® for Injection, 100 mg. There will be 3 cohorts, 11 subjects in each cohort. Subjects will be assigned to a cohort in a consecutive manner. In each cohort, 8 subjects will receive Modufolin® for Injection, 100 mg and 3 subjects will receive placebo. The IMP/placebo will be administered as a single dose on Study Day 1. The IMP/placebo will be administered in the morning and the time will be recorded in the CRF. The study subjects should be fasting overnight (8 hrs) before IMP/placebo administration until 4 hrs post-dose. There will be an interval of at least 7 days between each cohort to allow time for the iSRC to evaluate safety data before proceeding to the next dose level.

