### 17.4.3 Exposure-response analysis (Primary analysis)

The relationship between the plasma concentration of Modufolin® and change-from-baseline QTcF ( $\Delta$ QTcF) will be quantified using a linear mixed-effects modeling approach with  $\Delta$ QTcF as the dependent variable, plasma concentration of Modufolin® as the covariate, treatment (active or placebo) and time as categorical factors, and a random intercept per subject. The degrees of freedom for the model estimates will be determined by the Kenward-Rogers method. From the model, the slope (*i.e.*, the regression parameter for the

concentration) and the treatment effect-specific intercept (defined as the difference between active and placebo) will be estimated together with 2-sided 90% CI. The estimates for the time effect will be reported with degrees of freedom and SE.

The geometric mean of the individual  $C_{max}$  values for subjects in each of the active drug groups will be determined. The predicted effect and its 2-sided 90% CI for placebo-corrected change-from-baseline QTcF ( $\Delta\Delta QTcF$ ) (*i.e.*, the product with the slope estimate + treatment effect) at this geometric mean  $C_{max}$  will be obtained for each Modufolin® dose separately. If the upper bound of the 90% CI of the model predicted QTcF effect is below 10 msec at clinically relevant plasma levels of Modufolin®, it will be concluded that Modufolin® does not cause clinically concerning QTc prolongation.

The plot of the observed median-quantile Modufolin® concentrations and associated mean  $\Delta\Delta QTcF$  (90% CI) adjusted for diurnal effects together with the regression line presenting the predicted  $\Delta\Delta QTcF$  (90% CI) (as described in the publication by Tornoe et al.) will be used to evaluate the adequacy of the model fit to the assumption of linearity and the impact on quantifying the exposure response relationship. Additional exploratory analyses (via graphical displays and/or model fitting) will include accounting for a delayed effect (hysteresis) and the justification for the choice of pharmacodynamic model (linear versus nonlinear) as follows.

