#### 17.4.4 By-time point analysis:

The analysis for QTcF will be based on a linear mixed-effects model with change-from-baseline QTcF ( $\Delta QTcF$ ) as the dependent variable, time (categorical), treatment (Modufolin® for Injection, 100 mg and placebo), and time-by-treatment interaction as fixed effects, and baseline QTcF as a covariate. Subject will be included as a random effect for the intercept. Subject dosed with placebo will be analyzed as a pooled group. An unstructured covariance

matrix will be specified for the repeated measures at post-dose time points for each subject. If the model with unstructured covariance matrix fails to converge, other covariance matrix such as autoregressive and compound symmetry will be considered. From this analysis, the least-squares (LS) mean and 2-sided 90 % CIs will be calculated for the contrast “Modufolin® versus placebo” at each dose of Modufolin® and each post-dose time point, separately.

For HR, PR, and QRS intervals, the analysis will be based on the change-from-baseline values ( $\Delta$ HR,  $\Delta$ PR,  $\Delta$ QRS). The same model will be used as described for QTcF. The LS mean, SE and 90% CI from the statistical modeling for both change-from-baseline and placebo-corrected change-from-baseline values will be listed in the tables and graphically displayed.

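### Subjects are randomised only within consecutive dose cohorts, so the dose groups are not balanced as section 9.2 says; neither ECG model carries cohort, and the by-time-point dose contrasts bear most of the consequence

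*Protocol*

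**What the plan says.** Protocol 11.6 sets the allocation to dose: "Subjects will be assigned to a cohort in a consecutive manner". It adds "There will be 3 cohorts, 11 subjects in each cohort" and "There will be an interval of at least 7 days between each cohort". Each of the three planned cohorts has its own dose: 200, 350 or 500 mg/m². Section 10.8 then randomises within each cohort, 8 subjects to active and 3 to placebo.

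Section 9.2 describes the purpose differently: "Randomization will be used to minimize bias in the assignment of subjects to dose groups".

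The primary model in 17.4.3 regresses ΔQTcF on "plasma concentration of Modufolin® as the covariate, treatment (active or placebo) and time as categorical factors", "and a random intercept per subject". The by-time-point model in 17.4.4 has time, treatment, their interaction and baseline QTcF, and states "Subject dosed with placebo will be analyzed as a pooled group". It then gives a 90% CI for each dose against that pooled placebo at each time point. Neither list of terms includes cohort. Under the hysteresis heading of 17.4.3, hysteresis is explored only if an effect above 10 msec cannot be excluded by time point in the two highest dose groups.

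**The concern.** Randomisation within a cohort protects active against placebo in that cohort. It does not protect one dose against another, because dose follows the order of entry. If mean ΔQTcF differs between cohorts for reasons other than drug, such as intake of volunteers, season or staff, the models as written have no term to absorb it.

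In 17.4.4 each dose group of 8 is compared with 9 placebo subjects, of whom 6 come from other cohorts. A shift there looks like a dose effect. It could also hide one: a falsely excluded 10 msec effect in the two upper dose groups would mean that the hysteresis exploration is not triggered. In 17.4.3 the question is how much of such a shift reaches the predicted effect at the top-dose Cmax and its CI, on which the study's conclusion rests.

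**Working it through.** **The protocol's own power figure.** Inputs from 17.2: SD 7 msec, 24 active and 9 placebo, margin 10, true effect 3, one-sided 0.05. SE = 7·√(1/24 + 1/9) = 2.736. Power = Φ(7/2.736 − 1.645) = 82.0%, as stated. With 48 and 18 subjects the SE is 1.935 and power 97.6%, against a stated 97.5%.

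**By-time-point contrast (17.4.4).** Let c₁, c₂, c₃ be the cohort shifts in mean ΔQTcF. Three placebo subjects come from each cohort, so pooled placebo carries the mean shift c̄ and the contrast for dose d is biased by c_d − c̄.

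- Shifts −4, 0, +4: c̄ = 0, biases −4, 0, +4 msec.
- Shifts 0, 0, −5: c̄ = −1.67, biases +1.67, +1.67, −3.33 msec. The top dose then looks safer than it is.

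For random shifts with SD s (an assumption; the protocol gives none), the contrast gains SD s·√(2/3). The nominal SE is 7·√(1/8 + 1/9) = 3.40. Simulation used 40,000 runs, with variance pooled over the four groups:

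| s (msec) | added SD | true SD of contrast | mean model SE | 90% CI coverage | one-sided error |
|---|---|---|---|---|---|
| 0 | 0 | 3.41 | 3.37 | 89.9% | 5.1% |
| 2 | 1.63 | 3.77 | 3.40 | 86.6% | 6.5% |
| 3 | 2.45 | 4.19 | 3.44 | 83.0% | 8.4% |
| 4 | 3.27 | 4.70 | 3.48 | 79.0% | 10.6% |

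Estimating the variance from the two compared groups alone gives 6.4%, 8.0% and 9.8% for s = 2, 3 and 4.

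A concurrent-placebo contrast (8 v 3) restores 90% coverage, but its SE is 7·√(1/8 + 1/3) = 4.74. Per-dose power under the 17.2 assumptions falls from Φ(7/3.40 − 1.645) = 66% to Φ(7/4.74 − 1.645) = 43%.

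**Primary model (17.4.3), time-constant shift.** Assumptions: the 12 post-dose time points of Table 1; a biexponential concentration curve giving C(10 min) about 21,900 µg/L and AUC(0–4 h) about 13,900 h·µg/L at 500 mg/m² (Appendix 18.3, single dose: 23,300 and 13,600); within-subject covariance proportional to I + rJ, where r is the between/within variance ratio. The fixed shifts −4, 0, +4 were put through the generalised least-squares estimator, and the bias at the top-dose Cmax read off as treatment term plus slope × concentration:

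| r | no cohort term | with cohort term |
|---|---|---|
| 0.25 | +1.6 msec | 0 |
| 1 | +0.5 msec | 0 |
| 2 | +0.26 msec | 0 |

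The bias falls roughly as 1/(1 + 12r): 1.6 × 4 = 6.4, 0.5 × 13 = 6.5, 0.26 × 25 = 6.5. The shift cancels from the treatment term because the ratio is 8:3 in every cohort, and the slope rests mainly on the fall in concentration within each subject.

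Simulation with r about 1 (600 runs per scenario; Monte Carlo SE of coverage √(0.9·0.1/600) = 1.2 points):

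- No shift: model SE 2.58 with or without cohort, so the term costs nothing.
- Random shift SD 4, no cohort term: model SE 2.90 against an actual SD of 2.68, coverage 92%, false exclusion of 10 msec 4.8%.

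A separate 2,500-run simulation with a between-subject share of 0.4 put power at a true 3 msec at 86.4% with no shift, and at 83.1% and 80.7% for shift SD 3 and 4. With a cohort term it stayed at 86.4%.

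**Primary model, shift confined to the first hour.** Shifts of −4, 0, +4 (r = 1) bias the top-dose prediction by 4.4 msec without cohort and 4.3 msec with it. Random SD 4 gives 80% coverage and 11.5% false exclusion without cohort, 77% and 10.7% with it. A cohort main effect does not repair this case.

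**The case against.** The strongest reply is that nothing in the protocol points to a shift of 3–4 msec in change from baseline. Baseline is taken on the same day (17.4.1), so differences in absolute QTcF between intakes subtract out. ECGs are read centrally and blind, with one reader and one lead per subject (12.3.1). There is one site, with standardised meals and morning dosing. This stands: the shift sizes are assumptions, and zero is among them.

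It is also fair that the by-time-point contrasts do not decide the study, and that pooling placebo is a reasonable trade of some bias for precision. Both stand, and pooling need not be abandoned. The contrasts do, however, decide whether hysteresis is explored.

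On 9.2, one can say that the sentence goes on to speak of balance across treatment groups, and that other sections describe the scheme correctly. That makes the correction editorial, but the words on dose groups are still wrong for this design.

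A reader might go further and infer that cohort shifts corrupt the primary slope and make its CI falsely reassuring, or that a cohort term would cure any such problem. The calculations support neither. A time-constant shift leaves a small bias and a slightly wide interval; a shift confined to the period near Cmax would matter, but a cohort main effect does not remove it.

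**Conclusion.** The point holds in a limited form. Section 9.2 claims a balance between dose groups that consecutive cohorts cannot give, and neither ECG model contains the cohort within which subjects are randomised.

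The main exposure is in 17.4.4: a one-sided error of about 6.5%, 8% and 10–11% in place of 5%, if cohort shifts have SD 2, 3 or 4 msec. For the primary analysis the effect of a time-constant shift is small: about 0.2–1.6 msec at the top dose for shifts of −4, 0 and +4, against a 10 msec margin, with some lost power and an interval that errs towards caution under random shifts. The case for a cohort factor there is that it is virtually free and matches how the trial randomises, not that the primary conclusion is unsafe without it. All sizes rest on assumed shifts, the assumed variance split and a concentration curve scaled to Appendix 18.3.

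**What to change.** 1. In 17.4.3 and the synopsis, add cohort as a fixed factor to the primary model. State that it removes time-constant cohort shifts only, not a cohort-by-time shift near Cmax. Cost: two degrees of freedom with three cohorts (more if cohorts are added) and essentially no precision.
2. In 17.4.4, keep pooled placebo as the main contrast and add a sensitivity contrast of each dose against its concurrent placebo, stating the precision cost (8 v 3, SE about 4.74 against 3.40 msec). Cost: one table.
3. In 9.2, say that randomisation balances active against placebo within a cohort, and not the dose groups.

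Carry the first two into the SAP. Nothing changes in the conduct of the study.

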### 17.2 Determination of sample size

Assuming a 1-sided 0.05 significance level and a standard deviation of 7 msec for  $\Delta QTcF$ , a total of 33 evaluable subjects who complete Modufolin® (24 subjects) and placebo (9 subjects), separately will be sufficient to achieve 82% power to exclude a prolongation of 10 msec or longer of the upper 1-sided 95% CI of the mean  $\Delta\Delta QTcF$ , assuming that the prolongation is 3 msec at the geometric mean peak Modufolin® concentration. Under the same assumptions, a total of 66 subjects (48 Modufolin® and 18 placebo) will achieve 97.5% power.

Note that this calculation is conservative, since it does not take into account any gain in precision due to the use of all data of each subject with the help of a linear mixed effects model.

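### The primary concentration-QTc model has no random slope, so its 90% CI at the 350 and 500 mg/m² Cmax may be too narrow

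*Protocol*

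**What the plan says.** Section 17.4.3, repeated in the synopsis, models ΔQTcF on plasma concentration with "treatment (active or placebo) and time as categorical factors, and a random intercept per subject". It adds that "The degrees of freedom for the model estimates will be determined by the Kenward-Rogers method". No random slope is named, and nothing is said about the residual covariance of the serial ECGs.

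The ΔΔQTcF effect is then predicted at the geometric mean Cmax of each dose separately. The no-concern conclusion follows "If the upper bound of the 90% CI of the model predicted QTcF effect is below 10 msec at clinically relevant plasma levels". The checks listed in 17.4.3 concern linearity (including a two-sided 5% test of a quadratic term) and hysteresis. None looks at slope variation or serial correlation.

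For the by-time point model of the same ΔQTcF data, section 17.4.4 specifies an unstructured covariance, with this fallback: "If the model with unstructured covariance matrix fails to converge, other covariance matrix such as autoregressive and compound symmetry will be considered".

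**The concern.** A random-intercept model assumes a common slope. If the residuals are left independent, it also assumes that any two post-dose values of a subject are equally correlated, whether minutes or a day apart. Departures from either assumption enter the prediction at Cmax directly, because Cmax is the extreme of the concentration range. The random-intercept SE leaves them out. Kenward-Roger adjusts SEs and degrees of freedom within the stated covariance; it does not supply a missing variance component.

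The error runs in one direction: the upper bound comes out too low, and the trial would exclude a 10 msec effect more often than the nominal one-sided 5%. The predictions most exposed are those at the supratherapeutic levels, read here as 350 and 500 mg/m². Sections 7.1 and 9.2 rely on the supratherapeutic doses to do without a positive control. The quadratic-term test in 17.4.3 uses the same error structure, and a spurious rejection there could replace the primary model.

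**Working it through.** **1. The plan's own figure.** Section 17.2 gives the inputs: "Assuming a 1-sided 0.05 significance level and a standard deviation of 7 msec for" ΔQTcF; "a total of 33 evaluable subjects who complete Modufolin® (24 subjects) and placebo (9 subjects"); and "assuming that the prolongation is 3 msec at the geometric mean peak". The distance to the margin is 10 − 3 = 7 msec.

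- 24 against 9: SE = 7 × √(1/24 + 1/9) = 2.74; power = Φ(7/2.74 − 1.645) = 82.0% (stated 82%).
- 48 against 18: SE = 1.93; power = 97.6% (stated 97.5%).

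The stated power reproduces. It is a two-sample calculation and does not use the mixed model.

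**2. Where the slope information sits.** Post-dose ECG and PK times are 5, 15 and 30 min and 1, 2, 3, 4, 5, 6, 8, 12 and 24 h (Table 1). Appendix 18.3 gives, for the parent at 500 mg/m², C(10 min) 23300 µg/L and AUC(0–4h) 13600 h·µg/L, with a fast early phase and a terminal half-life of 1.5–1.8 h. These two values do not fix a curve: a one-phase fit is met by k = 2.68/h (half-life about 16 min) and also by k = 11.3/h. An assumed two-phase curve that meets both values is

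C(t) = 44·exp(−ln2·t/0.16) + 1.8·exp(−ln2·t/1.6) mg/L, t in hours.

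It gives C(10 min) = 23.0 mg/L and AUC(0–4h) = 13.6 h·mg/L. Relative to the 5 min value of 32.4 mg/L, it stands at 51% at 15 min, 20% at 30 min, 5% at 1 h and 2% at 2 h. The slope therefore rests on the first four points.

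**3. Simulation of the planned model.** There were 8 active subjects at each dose and 9 on placebo, 12 post-dose times, a REML random intercept, Satterthwaite df in place of Kenward-Roger, and 2000 runs per scenario. Total ΔQTcF SD was 7 msec before any slope variation was added.

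Assumptions that are not in the protocol:
- between-subject SD 5 msec (repeated with 3.5);
- log-SD of concentration 0.25;
- the slope SDs, given as SD of the drug effect at the 500 mg/m² Cmax;
- exponential serial correlation, with the time constants shown.

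The ratio r is the true SD of the prediction divided by the model SE. The table is for between-subject SD 5.

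| Slope SD (msec); correlation | r at 200 | r at 350 | r at 500 | 90% CI coverage at 500 | False exclusion at 500 |
|---|---|---|---|---|---|
| 0; none | 0.99 | 1.00 | 1.00 | 90.4% | 4.7% |
| 3; none | 1.00 | 1.01 | 1.03 | 89.4% | 5.8% |
| 5; none | 1.05 | 1.12 | 1.19 | 83.6% | 8.2% |
| 7; none | 1.08 | 1.21 | 1.35 | 77.2% | 12.6% |
| 0; 0.5 h | 1.04 | 1.11 | 1.17 | 84.6% | 8.2% |
| 0; 2 h | 1.05 | 1.12 | 1.18 | 84.3% | 8.2% |
| 5; 1 h | 1.08 | 1.21 | 1.33 | 79.4% | 10.5% |

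With between-subject SD 3.5 the pattern is the same and somewhat stronger. The combined case (5 msec, 1 h) gives r = 1.17, 1.32 and 1.42 at the three doses and 12.4% false exclusion at 500. At an exposure equivalent to 120 mg/m², r is at most 1.07 in any scenario.

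**4. Hand checks.** False exclusion is roughly Φ(−1.645/r): r = 1.19 gives Φ(−1.38) = 8.3%, and r = 1.33 gives Φ(−1.24) = 10.8%. For slope SD 5 the true SD is 3.25, against 2.71 without slope variation. The added variance is 3.25² − 2.71² = 3.2, close to 25/8 = 3.1. That is what averaging individual slopes over one cohort of eight would give.

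**5. Spread over other settings.** Runs with other PK curves, df and variance splits gave, at the 500 mg/m² Cmax:
- slope SD 3: 5.5–6.3%;
- slope SD 5: 8.1%;
- 1 h correlation: 8.2–8.9%, or 7.2% if half the within-subject variance is uncorrelated noise;
- slope SD 3 plus 1 h: 9.7–11.5%, or 7.9% with that noise.

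Under such departures the nominal 5% quadratic test rejected in about 8–14% of runs.

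**6. The remedy.** In 250 runs per scenario at the 500 mg/m² Cmax (between-subject SD 5, t with 25 df), a random slope raised coverage from 83.6% to 89.6% at slope SD 5. A serial residual raised it from 84.3% to 89.2% at 2 h. Both together raised it from 79.4% to 88.4% at 5 msec and 1 h.

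False exclusion with the random slope alone was 8.0% in that small set (Monte Carlo SE about 1.7 points). Sets of 500–900 runs gave 5.3% at slope SD 5 and 5.6% at SD 4. With neither problem present the random-slope model gave 4.6%.

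**The case against.** The main objection is that the size is assumed, and that stands. The protocol gives no slope SD and no correlation range. At a slope SD of 3 msec the planned interval is close to nominal. The reportable QTcF is a mean of medians from up to 10 replicates, so some within-subject variance is probably uncorrelated noise, which lowers the serial-correlation figures.

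A second objection also stands in part. The conclusion is tied to clinically relevant plasma levels, and section 9.2 expects a clinical dose of 120 mg/m², where the bias is almost nil. But 17.4.3 asks for a prediction at each dose. Appendix 18.3 also describes a high-exposure scenario of 750 mg per administration: 750/2 = 375 mg/m² at a body surface area of 2 m², and 750/1.5 = 500 mg/m² at 1.5 m². That falls where the SE is understated.

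Three stronger readings are tempting, and the documents do not support them.

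- **That 17.4.4 contradicts 17.4.3.** It does not. Its own fallback list includes compound symmetry, the same equal-correlation structure.
- **That the protocol has chosen independent residuals.** Section 17.4.3 is silent on residual covariance, which is ordinary SAP content. Only the random effect is fixed in the text.
- **That the wording in 17.2, "Note that this calculation is conservative, since it does not take into account any gain in precision", is wrong.** Under the stated SD of 7 the planned model's SE at the 500 mg/m² Cmax was 2.59–2.71 across settings, below 2.74; power at SE 2.59 is Φ(7/2.59 − 1.645) = 85%. Adding slope variance on top raises the total SD at Cmax to √(49 + 9) = 7.6 or √(49 + 25) = 8.6. That departs from the planning assumption and shows no error in it.

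**Conclusion.** The concern holds as a cheap improvement. The primary model fixes one common slope, and nothing else in the protocol protects the interval if that is untrue. Subject to the assumed inputs, false exclusion at the 500 mg/m² Cmax ranges from near nominal (slope SD 3 msec or less) to about 8% (slope SD 5), about 7–9% (1 h correlation) and roughly 8–11% for both. The harshest settings tried reached about 12–13%. At the 350 mg/m² Cmax, r is 1.11–1.32 once the 3 msec slope case is set aside. At 200 mg/m² it is at most 1.08 with between-subject SD 5 and 1.17 with 3.5.

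A reader might infer that the trial's safety conclusion is unreliable, or that its error rate is known to exceed 5%. Neither follows: if slopes are common and residuals uncorrelated, the planned interval is correct.

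**What to change.** In 17.4.3 and the synopsis, replace the single random effect with a subject-level random intercept and random slope on concentration, keeping Kenward-Roger df. State the fallback if the model does not converge: drop the intercept-slope covariance first, then the random slope. Use the same random effects when testing the quadratic term.

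A random slope does not deal with serial correlation. Add one sensitivity analysis with a residual correlation based on time, or a robust variance. Making a spatial residual part of the primary model is a trade-off in 33 subjects and can be left to the SAP.

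Leave 17.2 as it is.

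The change is a sentence or two and needs no extra data. When the slope term is not needed, the interval widens slightly (mean SE 2.63 against 2.58 msec in simulation). With 33 subjects the fallback may be used.
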